8.1.6. Supplementary analysis

A supplementary subgroup analysis will be performed on primary endpoints, for the following subgroups:

- Participants who had concomitant SCS rescue medications (identified with file provided by Sanofi containing CDGsn00010 medications) (Yes, No)
- Participants who have respected SABA washout period (only for untrimmed distal [s]iVaw)
- Removing data with technical issues (only for untrimmed distal [s]iVaw)

In these subgroup analyses, nominal p-value will be provided for descriptive purpose only.

Results will also be illustrated with forest plots.

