6.5 CONCOMITANT THERAPY

Any medication or vaccine (including over-the-counter or prescription medicines, vitamins, and/or herbal supplements) that the participant is receiving at the time of enrollment or receives during the study must be recorded along with:

- Reason for use.
- Dates of administration including start and end dates.
- Dosage information including dose and frequency.

Prohibited concomitant therapy:

- Any biologic therapy (including experimental treatments and dupilumab) or any other biologic therapy/immunosuppressant.
- Treatment with live (attenuated) vaccine.
- Treatment with systemic corticosteroids (systemic corticosteroids can only be used to treat an asthma exacerbation, and are not allowed to be used for other conditions)

During the FU period the asthma treatment will be administered based on Investigator's medical judgment and normal clinical practice.

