3. INVESTIGATIONAL PLAN

3.1. Overall study design and plan

This is a Phase IV, 2:1 randomized, parallel, multinational, multicenter study, with a 24-week double-blind placebo-controlled treatment period to assess the effect of dupilumab on airway inflammation through assessments of lung function, mucus plugging, and other lung imaging parameters in participants with asthma.

Approximately 97 participants will be randomly assigned to study intervention, in a 2:1 dupilumab to placebo ratio, such that approximately 87 evaluable participants complete the study, assuming a 10% dropout rate (approximately 58 in the active group and 29 in the placebo group). Randomization will be stratified by dose level (medium/high – no less than 40% in ‘high ICS’ stratum) of inhaled corticosteroids (ICS) and region (Eastern Europe (EE)/Rest of the World (ROW)). In total, no more than 40% participants should be in EE strata.

[figure not shown]
The study will comprise of:

- Screening period: 4 weeks (± 1 week), from signed informed consent to randomization (Day [-35, -21] to Day -1).
- Randomized, placebo-controlled treatment period: 24 weeks from baseline (Day 1).
- Post-treatment follow-up period: up to 12 weeks or until the participant switches to commercialized dupilumab (or other biologic product), whichever comes first.

Study duration for each participant will be a total of minimum 29 weeks and up to 41 weeks. A participant is considered to have completed the study if he/she has completed all phases of the study including the post treatment follow-up visit (V6).

The end of the study is defined as the date of the last visit of the last participant in the study.

Figure 3-1 Study plan

ACQ-7= 7-item Asthma Control Questionnaire; AQLQ(S) =Asthma Quality of Life Questionnaire with Standardized Activities; D=Day; FeNO= Fractional exhaled nitric oxide; FU= Follow-up; HRCT= High-resolution computed tomography; ICF=Informed Consent Form; mg=milligram; mL=milliliter; Q2W= every 2 weeks; R=Randomization; V=Visit

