7.1.2. Concomitant medications

Concomitant medications are any treatments received by the participant concomitantly to the IMP, starting from the 1st administration of IMP to the date of last administration +98 days.

The following concomitant medications summaries will be generated separately by study intervention group:

- Inhaled corticosteroids in combination with other controllers summarized by medication type (ICS, LABA, LAMA, LTRA, Other) and standardized medication name.
Note: These medications are recorded in the asthma controller medication eCRF page and ATC codes will be used to categorize them into ICS (ATC class R03BA), LABA (ATC class R03AC), LAMA (ATC class R03BB), LTRA (ATC class R03DC) or Other.
- Reliever (rescue) medications summarized by medication type (SABA, systemic corticosteroids, other) and standardized medication name (see [Section 15.13](#)).
Note: These medications are recorded in the asthma reliever medication eCRF page.
- Other concomitant medications.
Note: These medications are recorded in the other medications eCRF page.

The concomitant prohibited medications will also be presented by prohibited medication category as defined in deviation and standardized medication name (see [Section 15.9](#)).

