8.1.5. Sensitivity analysis

A sensitivity analysis on the two primary endpoints of achievement of FeNO <25 ppb at Week 24 and percent change from baseline to week 24 in untrimmed distal [s]iVaw at TLC will be carried out. For the latter, an analysis of covariance model (ANCOVA) with data from multiple imputation (MI) on missing results under an assumption of missing at random (MAR) will be used. For response of FeNO <25 ppb at week 24, a CMH testing procedure with data from multiple imputation (MI) on missing results under an assumption of missing at random (MAR) will be performed. Under this assumption, each missing score will be imputed 100 times and incorporated with non-missing data from 100 complete datasets. Each dataset will include FeNO / untrimmed distal [s]iVaw at baseline, week 4, week 12 (only for FeNO), and week 24, as well as relevant covariates specified below to support the analysis. Following steps will be conducted for this analysis. The number of imputations (100) will be informally verified by replicating sets of 100 imputations and checking whether the combined results are stable. If not stable, the number of imputations will be increased and informally checked as above, until stable estimates are obtained.

- Use the Markov chain Monte Carlo (MCMC) method to impute for intermittent missing values by study intervention group and to create 100 datasets with monotone missing pattern. According to the nature of the endpoint, minimum and maximum values will be specified in this imputation.
- For each of 100 datasets with monotone missing pattern created from MCMC imputation, use monotone regression method to impute remaining missing value by study intervention group up to week 24. In the imputation regression model, the following covariates will be included:
 - region (EE/ROW) and ICS dose level (medium/high)Percent change from baseline at week 24 and achievement of FeNO <25 ppb can be calculated with non-missing score or imputed score for every single participant in all datasets. All 100 datasets with full imputation for missing values will be input to the following models.

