15.12. Biomarkers

Fractional exhaled nitric oxide (FeNO) will be analyzed using a NIOX instrument using a flow rate of 50 mL/s, and reported in ppb. This assessment should be conducted prior to spirometry, FOT and HRCT scan and the participant should refrain from eating and drinking for at least 1 hour prior to the procedure.

15.13. Rescue and Prohibited Medications.

Rescue medications (ie, reliever medications) will be identified from the "Asthma Reliever Medication" eCRF page.

[figure not shown]
In the table summary, rescue medications will be categorized into SABA (ATC class R03AC), systemic corticosteroids (ATC class H02AB) or Other.

Treatment with the following medications is considered as prohibited:

- Immunosuppressants and biologic therapy within 3 months prior to V1 until EOT (V5)
- Treatment with live (attenuated) vaccine within 4 weeks before V1 until the end of study
- Treatment with systemic corticosteroids within 2 weeks prior to V1, during screening and randomized study intervention period. Systemic corticosteroids can only be used to treat an asthma exacerbation during the randomized study intervention period and are not allowed to be used for other conditions.

This page was left intentionally blank

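### The systemic-steroid Yes/No subgroup in SAP 8.1.6 is only a crude check on primary values taken inside the wash-out: it is not tied to the measurement date and it splits on a post-randomisation event (minor)

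*SAP*

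**What the plan says.** **Wash-out and fallback.** Protocol Table 4 (Section 8.1) sets 4 weeks for systemic corticosteroids. Protocol 6.6 applies this to HRCT and FeNO, the sources of both primary endpoints. After an exacerbation treated with SCS, a visit may be moved by up to 1 week. If that is not possible, the tests proceed and the recent steroid use is recorded. Dates and times of rescue medication must be recorded.

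**Analysis.** SAP Section 8 uses all collected efficacy values except those after a COVID-19 discontinuation. SAP Tables 2-2 and 4-2 name only treatment discontinuations as intercurrent events.

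**Supplementary items.** SAP 8.1.6 lists, for both primary endpoints, "Participants who had concomitant SCS rescue medications", split Yes or No from a sponsor medication file. The next item, for [s]iVaw only, is "Participants who have respected SABA washout period". For these subgroups a "nominal p-value will be provided for descriptive purpose only".

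**Meaning of concomitant.** SAP 7.1.2 defines concomitant medication as "starting from the 1st administration of IMP to the date of last administration +98 days". For the time after treatment, Protocol 6.5 says: "During the FU period the asthma treatment will be administered based on Investigator's medical judgment and normal clinical practice".

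**The concern.** A reader of the primary results may reasonably ask whether FeNO or airway-volume values measured soon after a steroid course moved them. The SCS subgroup is the nearest visible analysis, and it has two weaknesses for that purpose.

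- **Timing.** A course in Week 6 and a course five days before the Week 24 test both count as Yes, although only the second falls inside the wash-out at Week 24.
- **Selection.** SCS rescue happens after randomisation and follows exacerbations, which Protocol Section 2 says dupilumab reduces. Participants who avoid rescue on placebo are therefore a more selected group than those who avoid it on dupilumab, so neither stratum keeps the randomised comparison.

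No confirmatory test depends on this. What is at stake is whether a supplementary analysis, shown in a forest plot, can answer the question it will be read as answering.

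**Working it through.** The documents state no figure for SCS use, so there is nothing to reproduce and every size below rests on assumptions.

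**Assumptions.** 97 randomised 2:1, taken as 65 dupilumab and 32 placebo. SCS use over 24 weeks (168 days) is 20-30% on placebo and 10-12% on dupilumab, with one course per user, spread evenly.

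**1. Which courses leave a value inside the wash-out.** With a 28-day wash-out and a 7-day postponement, the last steroid must be at least 28 - 7 = 21 days before the planned visit. If the +3-day visit window is used as well, this becomes 18 days. With no postponement it is 28 days.

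**2. Participants inside the window at Week 24.** Expected number = 32 × p_placebo × w/168 + 65 × p_dupilumab × w/168.

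| w (days) | 20% / 10% | 30% / 12% |
|---|---|---|
| 18 | 1.4 | 1.9 |
| 21 | 1.6 | 2.2 |
| 28 | 2.2 | 2.9 |

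**3. Size of the Yes group.**
- Counted to Week 24: 32 × 0.20 + 65 × 0.10 = 12.9, up to 32 × 0.30 + 65 × 0.12 = 17.4. The in-window share is w/168, or 11-17%.
- If the SAP 7.1.2 definition applies, counting runs to about Day 253 (a Week 22 last dose on Day 155, plus 98). At a constant rate, 1 - (1 - p)^1.5 gives 28.4-41.4% on placebo and 14.6-17.4% on dupilumab, so 18.6-24.6 participants. The in-window share is then 7-12%. Of that period, 253 - 169 = 84 days, or 33%, lie after Week 24.

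**4. Possible movement in FeNO response.** If every in-window placebo response were caused by the steroid, and no dupilumab response were, the difference would shrink by up to 30% × 21/168 = 3.75 points, or 30% × 28/168 = 5.0 points. In the opposite case it would be inflated by up to 12% × 21/168 = 1.5 points, or 12% × 28/168 = 2.0 points.

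**5. Selection bias in the No stratum for [s]iVaw.** Let r = 0.2-0.4 (assumed) be the correlation between exacerbation-proneness and a poorer [s]iVaw change. With p the fraction rescued and z its normal cut-off, mean proneness among the non-rescued is -φ(z)/(1 - p). Bias = -r × (dupilumab mean - placebo mean).
- To Week 24, smallest (20% / 12%): -0.2 × (-0.227 + 0.350) = -0.025 SD.
- To Week 24, largest (30% / 10%): -0.4 × (-0.195 + 0.497) = -0.121 SD.
- To Week 36: -0.032 to -0.159 SD.

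The sign is against dupilumab throughout.

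**6. Precision, in SD units.**
- All randomised: √(1/32 + 1/65) = 0.216.
- No stratum: 0.237-0.249 (Week 24 count) or 0.248-0.268 (Week 36 count), which is 10-24% larger.
- All randomised with flagged Week 24 values removed: 0.218-0.220, about 1-2% larger.

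The largest bias is about half of the No-stratum standard error to Week 24, and 0.6 of it in the worst Week 36 case.

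**7. Illustrative simulation for a binary response.** Treatment had no effect on response, severity drove both rescue and non-response, and treatment lowered the odds of rescue (odds ratio 0.5 or 0.3). The overall odds ratio was 1.00, but the stratum odds ratios were 0.86-0.95 in Yes and 0.90-0.96 in No.

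**The case against.** **The SAP never calls this item a wash-out check.** That is true. The adjacent SABA item names a wash-out and the SCS item does not, so the two may serve different purposes. It follows that no visible SAP analysis is directed at in-wash-out primary values: the technical-issues item is undefined and covers [s]iVaw only, and SAP 8.1.5 addresses missing data.

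**The No stratum is informative.** This stands in part. If the file finds all SCS users, that stratum contains no in-window post-baseline value. It is a crude exclusion, confounded and less precise, and it would be wrong to call it useless.

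**Readings that go too far.**
- *The primary analysis is wrong.* Using these values is a coherent treatment-policy choice; it is only left unnamed.
- *Courses after Week 24 count as Yes.* This depends on whether SAP 7.1.2, written for medication summaries, governs an efficacy subgroup. SAP 5.1 counts rescue within the treatment period, and neither the identifying file nor the table shells are visible.
- *The 4-week wash-out contradicts the 1-week postponement.* The protocol gives a sequence with a stated fallback, so no contradiction is shown.
- *Baseline is certainly clear.* SAP 15.13 treats as prohibited "Treatment with systemic corticosteroids within 2 weeks prior to V1, during screening and randomized study intervention period", but protocol criterion E15 names only oral steroids before V1. An intramuscular or intravenous dose just before V1, followed by a 21-day screening period, would leave fewer than 28 days.

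**Few values are affected and the p-values are descriptive.** Both are true, and they set the severity. The label does not remove bias from the plotted estimates. The SABA item is also a post-randomisation subset, so it is a precedent for using wash-out timing and not a model of a randomised comparison.

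**Conclusion.** The point holds as a minor, cheap improvement. The SCS Yes/No split is a crude, selection-prone and imprecise check on whether in-wash-out values influence the primary results. Under the assumed rates and even timing, about 1 to 3 participants are in the window at Week 24, and they are a small part of the Yes group. The bias in the No stratum is at most about 0.12 SD (0.16 SD if rescue is counted to Week 36) and runs against dupilumab. Different SCS rates, clustered courses or a date rule in the unseen file would change these sizes. The primary tests and the error control are untouched.

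**What to change.** 1. Keep the primary analysis. In SAP Tables 2-2 and 4-2, name treatment policy as the strategy for SCS rescue.
2. In SAP 8.1.6, derive a per-measurement flag for SCS use within the protocol's own wash-out, from the recorded dates. Apply it to baseline and post-baseline values. Add a rule for partial dates, because SAP 15.4.3 imputes none.
3. Replace the Yes/No split, or keep it only as a labelled non-randomised description. In its place, run one supplementary analysis of all randomised participants with flagged post-baseline values set to missing. Use the existing MMRM for [s]iVaw. For FeNO use the method in SAP 8.1.5: "a CMH testing procedure with data from multiple imputation (MI) on missing results under an assumption of missing at random (MAR) will be performed".
4. Compare the FeNO run with the 8.1.5 result and not with the primary. The SAP plans "such that approximately 87 evaluable participants complete the study, assuming a 10% dropout rate", so 97 - 87 = 10 dropouts may count as non-responders in the primary and would swamp the few flagged values.
5. Label the run a hypothetical-strategy analysis, and state that missing at random is doubtful because SCS follows an exacerbation.

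The flag follows the protocol's wash-out text; no clinical rule is proposed.

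**Cost.** One derived flag with a partial-date rule, one supplementary run and a short table entry. Under the assumed rates, 1.4-2.9 scans at each of Weeks 4 and 24, about 3-6 of up to 97 × 2 = 194, become missing in that run only. The standard error of the Week 24 contrast rises by about 1-2%.

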8.1.7. Impact of Covid-19 pandemic

During the Covid-19 pandemic, a business continuity plan (BCP) was put in place to minimize the impact of the clinic visit interruption, ensure IMP treatment continuity and data collection. Direct to participant delivery of IMP from the site(s) and home injection(s) done by qualified site personnel and/or health care professionals for study drug administration were made available, where allowed by local regulations and approved by the participant, as planned per protocol. IMP permanent discontinuation due to Covid-19 pandemic is therefore expected to be minimum. Site(s) can update/correct the schedule of completion if visit is rescheduled/delayed – unless site staff cannot access vendor platform to update scheduled dates.

Missing data due to Covid-19 pandemic is likely to be missing at random. Therefore, the primary analysis using MMRM can adequately address this type of missing data. Participant disposition summaries by visit according to trial impact (disruption) due to COVID-19 overall and by country are already mentioned in [Section 5.1](#) of this SAP.

8.2. Secondary efficacy endpoints

8.2.1. Lung function measured by spirometry

Pre-BD FEV₁ and Post-BD FEV₁ (see [Section 15.9](#)) will be summarized in terms of actual value and change from baseline at baseline and at week 24.

In addition, at each post-baseline visit, the change from baseline will be modelled using an MMRM model under the missing at random framework. The MMRM model will include study intervention (dupilumab, placebo), baseline value of the parameter, region (EE/ROW), ICS dose level (medium/high), visits (up to week 24), age (years), height (cm), gender (male/female), study intervention by visit interaction, and baseline value of the parameter by visit interaction terms all as fixed effects. An unstructured (UN) correlation matrix will be used to model the within-participant errors.

The same strategy as for MMRM model for primary endpoint untrimmed distal [s]iVaw will be used for the selection of the covariance structure if MMRM under unstructured correlation matrix fails to achieve convergence.

8.2.2. Fractional Exhaled Nitric Oxide (FeNO)

FeNO (see [Section 15.12](#)) will be summarized in terms of actual value and change from baseline at Week 24).

In addition, at each post-baseline visit, the change from baseline will be modelled using the same MMRM model as the one used for the secondary endpoint relating to pre-BD and post-BD FEV₁. LS mean of each study intervention group, LS mean difference between the dupilumab and placebo groups, and the corresponding SEs and 95% CIs will be provided at all scheduled visits. The p-value corresponding to the LS mean difference will be provided at Week 24 only. FeNO data may be logarithmically transformed prior to analysis if extreme skewness was observed based on blinded data review.

The same strategy as for MMRM model for primary endpoint untrimmed distal [s]iVaw will be used for the selection of the covariance structure if MMRM under unstructured correlation matrix fails to achieve convergence.

8.2.3. Functional Respiratory Imaging (FRI)

FRI secondary endpoints (see [Section 15.10](#)) will be summarized in terms of actual value and change from baseline or percent change from baseline to each post-baseline visit (Week 4 and Week 24).

In addition, at each post-baseline visit, the change from baseline or percent change from baseline will be modelled using the same MMRM model as the one used for the primary end point relating to untrimmed distal [s]iVaw at TLC. Baseline value will be the one of the variable being analyzed and, in case of variables in the percentage scale, it will be the baseline value on the raw scale. LS mean of each study intervention group, LS mean difference between the dupilumab and placebo groups, and the corresponding SEs and 95% CIs will be provided at all scheduled visits. The p-value corresponding to the LS mean difference will be provided at Week 24 only.

The same strategy as for MMRM model for primary endpoint untrimmed distal [s]iVaw will be used for the selection of the covariance structure if MMRM under unstructured correlation matrix fails to achieve convergence.

FRI secondary endpoints are the following:

- Untrimmed distal [s]iVaw at FRC (percentage change from baseline)
- Trimmed distal [s]iRaw at TLC (percentage change from baseline)
- Trimmed distal [s]iRaw at FRC (percentage change from baseline)
- Global lung iVlobes at TLC (percentage change from baseline)
- iV/Q at TLC (change from baseline) for lower and upper lung
- HRCT based IAD (change from baseline) for lower and upper lung
- Global lung UCSF mucus scoring (change from baseline)

* Data may be logarithmically transformed prior to analysis if extreme skewness was observed based on blinded data review.

8.2.4. Asthma Control Questionnaire (ACQ-7)

ACQ-7 score (see [Section 15.8](#)) will be summarized in terms of actual value and change from baseline at baseline and at each post-baseline visit (Week 4 and Week 24).

In addition, at each post-baseline visit, the change from baseline will be modelled using MMRM model including study intervention (dupilumab, placebo), baseline value of the score, region (EE/ROW), ICS dose level (medium/high), visits (up to Week 24), study intervention by visit interaction, and baseline score by visit interaction terms all as fixed effects. An unstructured correlation matrix will be used to model the within-participant errors. LS mean of each study intervention group, LS mean difference between the dupilumab and placebo groups, and the corresponding SEs and 95% CIs will be provided at all scheduled visits. The p-value corresponding to the LS mean difference will be provided at Week 24 only.

The same strategy as for MMRM model for primary endpoint untrimmed distal [s]iVaw will be used for the selection of the covariance structure if MMRM under unstructured correlation matrix fails to achieve convergence.

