4.4.2. Visit naming conventions

The electronic Case Report Form (eCRF) visit label will be used to classify the assessments.

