8. EFFICACY ANALYSIS

Efficacy analyses will be performed on the ITT analysis set.

Participants will be analyzed for efficacy according to the study intervention group to which they are allocated by the IRT according to the randomization schedule at the randomization visit (as randomized), irrespective of the study intervention actually received.

For all efficacy analyses, time window will be used to assign the visit (see [Section 15.5](#)).

For the analysis of primary objective in the study intervention period,

- The null statistical hypothesis tested is that 1) the proportion of participants achieving response of FeNO <25 ppb at Week 24 is the same between dupilumab and placebo group; 2) the percentage change from baseline in untrimmed distal [s]iVaw is the same between dupilumab and placebo group.
- The alternative statistical hypothesis tested is that 1) the proportion of participants achieving response of FeNO <25 ppb at Week 24 is different between dupilumab and placebo group; 2) the percentage change from baseline in untrimmed distal [s]iVaw is different between dupilumab and placebo group.

In order to preserve the type I error at 0.05 level for the two primary endpoints, a hierarchical testing procedure will be adopted. The tests will be performed in this order:

1. Proportion of participants achieving response of FeNO <25 ppb at Week 24
2. Percentage change from baseline to Week 24 in untrimmed distal [s]iVaw at TLC

All efficacy measurements collected during the study will be considered for analyses, including those obtained after IMP discontinuation, except if study intervention discontinuation was due to the COVID-19 pandemic. Refer to [Table 2-2](#) for more details.

For efficacy endpoints where a change from baseline or percent change from baseline is assessed, only the participants with a baseline and at least one post-baseline value available will be included in the analysis model (number of participants included in the analysis model reported in the table). All available results will be included in the descriptive statistics.

Line plots for change and percent change from baseline will be presented by study intervention group, displaying the LS mean and SE at each visit. These plots will be provided for the primary and all secondary continuous endpoints.

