15.3. Missing efficacy data

Asthma Control Questionnaire (ACQ-7, ACQ-6 and ACQ-5)

- Based on the manual of ACQ (2), any more than one missing value is not acceptable. If more than one of the questions have missing value, the global score is invalid and will be considered as missing. If only one question has missing score, it will be interpolated (pro-rated) using the completed questionnaires from the previous visit. For instance, answer to question 5 is missing at Visit 4, and all questions are completed at Visit 3. Then the question 5 score at Visit 4 is interpolated as: (sum of score at Visit 4/sum of scores excluding question 5 at Visit 3) × score of question 5 at Visit 3. If the questionnaire from the previous visit is not complete either, the missing value will be imputed as the average of the completed questions within the current visit.

Asthma Quality of Life Questionnaire (AQLQ)

- To have a valid overall score, it is not acceptable to have more than three missing responses or more than one missing response per domain. For responses with more than acceptable amount of missing value(s), the overall score will be considered as missing. For responses with amount of missing value(s) within accept range, the missing score will be interpolated using the previous completions of the questionnaire following the similar algorithm used for ACQ.

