15.5. Visit windows

The analysis window below “[in brackets]” will be applied to post-baseline measurements to allocate them to a scheduled visit for the parameter (see [Appendix 15.2](#) for details of scheduled visits).

Table 15-2 Analyses window definition

Scheduled visit post-baseline	Targeted study day*	Visit window		
		AQLQ(S)	FRI and ACQ	Biomarkers, Forced Oscillometry, Spirometry and Vital signs
Week 4 (Visit 3)	29		[2, 98]	[2, 56]
Week 12 (Visit 4)	85			[57, 126]
Week 24 (Visit 5)	169	[2, ∞]	[99, ∞]	[127, ∞]

* The reference day (denoted as Day 1) for the calculation of study day will be the day of the first administration of IMP (except for participants randomized but not exposed). (See [Section 4.4.6](#)).

After applying the above time windows, if multiple assessments are associated to the same time point, the closest from the targeted study day will be used. In case of equality, the last measurement will be used. Re-allocated scheduled visits (ie, visit numbers) should be sequential if ordered by the date of measurement.

If there is no measurement available for a given parameter in an analysis window, data is considered missing for the corresponding visit.

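### The protocol schedule and SAP 15.3 indicate that ACQ-7 is collected at Week 12, but SAP 8.2.4 and Table 15-2 give it no Week 12 visit, so a Week 12 score is dropped or analysed as Week 4

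*SAP*

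**What the plan says.** - **Collection.** The ACQ-7 row of the schedule in protocol 1.3 carries five marks, as does the vital signs row: screening, baseline, Week 4, Week 12 and Week 24. SAP 15.3 explains how a single missing ACQ item is filled with a case in which the "answer to question 5 is missing at Visit 4, and all questions are completed at Visit 3". Table 15-2 equates Visit 3 with Week 4 and Visit 4 with Week 12.
- **Analysis visits.** SAP 8.2.4 summarises ACQ-7 as actual value and "change from baseline at baseline and at each post-baseline visit (Week 4 and Week 24"). It also promises LS means at all scheduled visits, with a p-value at Week 24 only.
- **Windows.** SAP Table 15-2 has columns for AQLQ(S), for FRI and ACQ together, and for biomarkers, oscillometry, spirometry and vital signs together. Its rows read "Week 4 (Visit 3) 29 [2, 98] [2, 56]", "Week 12 (Visit 4) 85 [57, 126]" and "Week 24 (Visit 5) 169 [2, ∞] [99, ∞] [127, ∞]". The Week 12 row has one window, which belongs to the last column.
- **Allocation rules.** SAP 8: "For all efficacy analyses, time window will be used to assign the visit". SAP 15.5: "if multiple assessments are associated to the same time point, the closest from the targeted study day will be used". SAP 4.4.2 has a competing rule, that the eCRF "visit label will be used to classify the assessments".

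**The concern.** The FRI windows suit imaging, because HRCT is done at Day 1, Week 4 and Week 24 and there is no Week 12 scan. ACQ shares that column although two places indicate that it does have a Week 12 visit. A score with no window of its own is absorbed by a neighbour.

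ACQ-7 change at Week 24 is a named secondary endpoint, analysed by MMRM under missing at random. For a participant with no Week 24 score, the model relies on that participant's earlier scores, and the Week 12 score is the closest of them in time. Dropping it loses information, leaves no Week 12 estimate, and lets some Week 12 scores enter the Week 4 mean.

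**Working it through.** **1. Reproduce the windows.** The limits in Table 15-2 are midpoints between target days.

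- Two visits (Days 29 and 169): (29 + 169)/2 = 99, giving [2, 98] and [99, ∞]. This is the FRI and ACQ column.
- Three visits (Days 29, 85 and 169): (29 + 85)/2 = 57 and (85 + 169)/2 = 127, giving [2, 56], [57, 126] and [127, ∞]. This is the spirometry and biomarker column.

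Both match the table exactly, so the ACQ windows are those of a measure taken at Weeks 4 and 24 only.

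**2. Place a Week 12 ACQ.** Protocol 1.3 allows ±3 days, and postponement of up to one week after a severe exacerbation treated with systemic corticosteroids.

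- Week 12: 85 ± 3 = Day 82 to 88; postponed, up to 88 + 7 = Day 95. All of these lie inside [2, 98].
- Week 4: 29 ± 3 = Day 26 to 32; postponed, up to Day 39.

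**3. Apply the closest-to-target rule (target Day 29).**

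| Score | Distance from Day 29 |
|---|---|
| Week 4 | at most 39 − 29 = 10 days |
| Week 12 | at least 82 − 29 = 53 days |

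With visits on these dates, a Week 12 score never displaces a Week 4 score. If Week 4 was missed and nothing else lies closer to Day 29, the Week 12 score becomes the Week 4 value. At the target day it is 85 − 29 = 56 days, or eight weeks, late.

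**4. Size of the information loss.** The documents give no within-participant correlations for ACQ-7, so these are assumptions. For correlations a (W4–W24), b (W12–W24) and c (W4–W12):

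- Week 4 only: R² = a²
- Weeks 4 and 12: R² = (a² + b² − 2abc)/(1 − c²)
- Variance of the Week 24 mean under monotone missingness with missing fraction m: proportional to R² + (1 − R²)/(1 − m)

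SAP 3.1 assumes 10% dropout, so m = 0.10.

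| c, a, b | R², W4 only | R², W4 + W12 | Relative variance, W4 only | Relative variance, W4 + W12 | Reduction |
|---|---|---|---|---|---|
| 0.5, 0.4, 0.6 | 0.16 | 0.37 | 1.093 | 1.070 | 2.2% |
| 0.6, 0.5, 0.7 | 0.25 | 0.50 | 1.083 | 1.056 | 2.6% |
| 0.7, 0.6, 0.8 | 0.36 | 0.64 | 1.071 | 1.040 | 2.9% |

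In standard error terms, 1 − √(1 − 0.022) = 1.1% and 1 − √(1 − 0.029) = 1.5%. At m = 0.20, a level the documents do not state, the variance reduction would be 4.4% to 6.1%. For the assumed correlations these are upper limits, because the formula credits every participant without a Week 24 score with a Week 12 score. Anyone who leaves before Week 12 has none.

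**The case against.** The strongest reply is that Week 12 collection is not certain. As extracted, the SAP copy of the schedule (15.2) has four ACQ-7 marks and none in the Week 12 position. SAP 8.2.4 and Table 15-2 agree with it, and the windows are exactly those of a two-visit schedule. On that reading the SAP holds a consistent position, and the Visit 4 case in 15.3 is only an illustration of a scoring rule. This stands in part, so the consequences above are conditional on collection. It does not remove the point. The same extracted table shows four FeNO marks where the protocol has five, so its counts are weak evidence. A real omission there would itself contradict the protocol schedule and SAP 15.3, while SAP 13 declares no change to the planned analysis.

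The eCRF label rule in SAP 4.4.2 would keep a Week 12 score from being relabelled. But SAP 8 gives windows precedence for efficacy, and 8.2.4 names no Week 12 visit in any case.

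Two stronger readings are tempting and unsupported.

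- A reader might infer that the windows split ACQ-7 from its own item 7, because on Days 99 to 126 an ACQ counts as Week 24 and same-day spirometry as Week 12. SAP 15.8 defines ACQ-7 as one score with item 7 converted from percent-predicted FEV₁. Nothing says that item 7 is taken from window-reassigned spirometry. The two endpoints can carry different visit labels, but the score is not broken up.
- A reader might infer that the Week 24 result is materially compromised. Observed Week 24 scores are untouched. Participants who stop treatment are asked to attend through Visit 5, and early-discontinuation visits include the ACQ, which limits missingness further.

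**Conclusion.** The inconsistency is real and its consequence is modest. The protocol schedule and SAP 15.3 point to a Week 12 ACQ-7; SAP 8.2.4 and Table 15-2 make no place for one. If it is collected on the permitted dates, the window rule discards it for every participant who has a Week 4 score and mislabels it as Week 4 for those who do not. The exception is a visit delayed past Day 98 under the emergency provisions of protocol Appendix 9; that score would fall in the Week 24 window.

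ACQ-7 is outside the testing hierarchy, since SAP 8.2.5 lists only the mucus score and trimmed distal [s]iRaw at TLC among the secondary endpoints. No confirmatory conclusion is at risk. The gain in Week 24 precision is at most about 2–3% in variance, on assumed correlations and 10% dropout. The better reasons to act are that collected data should not be dropped or relabelled by a grouping in a table, and that the documents should agree on when the instrument is given.

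**What to change.** Before database lock, which SAP 1 allows:

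1. In Table 15-2, move ACQ from the FRI column to the three-visit windows already defined: Week 4 [2, 56], Week 12 [57, 126], Week 24 [127, ∞].
2. In SAP 8.2.4, add Week 12 to the post-baseline visits, and state that all three visits enter the ACQ MMRM.
3. Align the ACQ row of the SAP schedule (15.2) with the protocol schedule. If the eCRF shows that ACQ is not collected at Week 12, say so and correct the protocol schedule and the 15.3 example instead.

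The cost is a few SAP edits and a small programming change, with no new data. There is one downside: an early-withdrawal ACQ on Days 99 to 126 would count as Week 12 rather than Week 24, leaving Week 24 missing for that participant unless a later score exists. Spirometry and FeNO are already handled that way.
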